### 6.3.2 Adverse Events by Preferred Terms

All AEs recorded in the CRF will be classified by body organs and terms under the classification standard of MedDRA (The most update version of MedDRA at the time of conducting data analysis will be used; the first level is System Organ Class (SOC) and the second level is Preferred Term (PT)) terms, and all AEs excluding the AEs whose causal relation with Fluarix Tetra is ‘Not-Related’ will be treated as AEs whose causal relation cannot be excluded (hereafter “Adverse Drug Reaction (ADR)”).

- ① The number of subjects and the number of AE/ADR, Serious AE/Serious ADR, Unexpected AE/ADR, Unexpected Serious AE/Serious ADR and Unexpected non-serious AE/ADR will be calculated according to the preferred terms. Also, the incidence proportion and its 95% confidence interval using the exact method will be estimated.
- ② Preferred terms of Serious AE/Serious ADR, unexpected AE/ADR will be presented respectively according to the proportion of AE in the local product document.
- ③ For Non-safety analysis set, the number of subjects and the number of AE/ADR, Serious AE/Serious ADR, Unexpected AE/ADR, Unexpected Serious AE/Serious ADR and Unexpected non-serious AE/ADR will be calculated according to the preferred terms. Also, the incidence proportion and its 95% confidence interval using the exact method will be estimated.
- ④ The number and percentage of AE according to the maximum intensity, outcome, relationship to marketed vaccine/product, medically attended visit will be calculated.
- ⑤ All AEs will be classified into the preferred terms according to the maximum intensity, outcome, relationship to marketed vaccine/product, medically attended visit. Also, the number and percentage of each AE will be calculated.

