2. OBJECTIVE

- To assess the safety of GSK Vaccines' quadrivalent seasonal influenza vaccine D-QIV, *Fluarix Tetra*, in terms of frequency and intensity of AEs and SAEs when administered according to the local PI in adults and children from six months of age in Korea.

Refer to Section 10.1 for the definition of the endpoints (AE and SAE).

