10.5.2.1. Within group assessment

The AEs/***ADRs/SAEs*** will be analysed in the drug use investigation report according to the expectedness and unexpectedness criteria (Refer to ***GLOSSARY OF TERMS*** for the definitions of expected AEs and unexpected AEs).

The number and percentage, with exact 95% CI, of any AEs, ADRs ***and SAEs*** occurring within 21 days (Day 0 to Day 20) will be tabulated for the number of subjects receiving *Fluarix Tetra*.

The verbatim reports of signs and symptoms will be matched and coded according to the appropriate WHOART PT. The drug use investigation physician will review and confirm the appropriate WHOART PT by responding to data queries if any discrepancies are reported while coding. The percentage of subjects with AEs, ADRs, and ***SAEs*** occurring within 21 days (Day 0 to Day 20) with its exact 95% CI will be tabulated by PT.

The outcome of pregnancy (reported in the pregnancy report form) for subjects who were pregnant at the time of vaccination and those who become pregnant within 21 days after vaccination will be presented, if possible.

SAEs reported during the drug use investigation period [each subject receiving the vaccine up to 21 days (Day 0 to Day 20) after vaccination and for pregnant subjects until 6-8 weeks after delivery] will be described in detail, if possible.

The incidence proportion of AEs as overall and by age group and gender will be measured with the exact 95% CI. An exploratory comparison between these groups will be performed using Chi-square exact test with the statistical significance level 0.05.

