## 4. Endpoint

### 4.1 Safety Endpoint

- Occurrence of expected and unexpected AEs during the 21 days (Day 0 to Day 20) follow-up period after vaccination
- Occurrence of SAEs starting from the date of vaccination in the drug use investigation up to 21 days (Day 0 to Day 20) after vaccination of the subject in the drug use investigation

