### 6.3 Safety Analyses

Safety analysis on safety parameter will be done on safety analysis set.

In the safety analysis set, the number of subjects to whom AE occurred and the number of AEs will be calculated. Also, the incidence proportion of AEs and its 95% confidence interval will be estimated.

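### Intensity is part of the objective, but the plan's text reports it only as a number and percentage of AEs, with no proportion of vaccinees and no CI

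*SAP*

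**What the plan says.** Protocol section 2 and SAP 1.2 set one objective: safety "in terms of frequency and intensity of AEs and SAEs when administered according to the local PI". The endpoints are narrower and speak of occurrence only, for example "Occurrence of expected and unexpected AEs during the 21 days (Day 0 to Day 20) follow-up period after vaccination" (SAP 4.1; Protocol 10.1 is equivalent).

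Frequency is planned at subject level:

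- SAP 6.3, all AEs together: "Also, the incidence proportion of AEs and its 95% confidence interval will be estimated".
- SAP 6.3.2, item 1, by PT for AEs/ADRs and their serious and unexpected subsets. It names subjects and events as separate counts and then adds: "Also, the incidence proportion and its 95% confidence interval using the exact method will be estimated".
- Protocol 10.5.2.1: "The incidence proportion of AEs as overall and by age group and gender will be measured with the exact 95% CI". The same section tabulates AEs, ADRs and SAEs by PT on a subject basis, in a sentence that begins "The percentage of subjects with AEs, ADRs, and". It has no row for intensity.

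Intensity appears in two places only. SAP 6.3.2, item 4, says: "The number and percentage of AE according to the maximum intensity, outcome, relationship to marketed vaccine/product, medically attended visit will be calculated". Item 5 repeats this by PT and ends: "Also, the number and percentage of each AE will be calculated". Neither item mentions subjects, an incidence proportion or a CI.

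**The concern.** A percentage of AE records is a different quantity from a risk per vaccinee. It falls when more mild events are written on diary cards, even if severe events are unchanged. It also counts a subject once for every event. A reader who wants to know what proportion of vaccinees had a Grade 3 AE, and how precisely that is known, would not find the answer in the analyses as written.

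The SAE tables do not supply it. Protocol 7.2.2.2 states that Grade 3 rates intensity and must not be confused with seriousness. A Grade 3 event that is expected and not serious enters the subject-level tables only as an AE or ADR of any grade, together with the mild ones.

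The missing quantity is also the kind for which the study's precision was set out. Protocol Table 4 gives exact intervals for a percentage of subjects at 600 per group.

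**Working it through.** **Inputs.** From Protocol 10.2 and Table 4: n = 600 per group, two-sided 95%, exact method. From Protocol 10.2: 720 enrolled per group with 20% dropout assumed, so 720 × 0.8 = 576 as a lower value of n. The documents give no rate of Grade 3 AEs and no expected number of AE records, so the counts used for these below are assumptions.

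**Formula.** Clopper-Pearson for x subjects out of n: lower limit = Beta(0.025; x, n − x + 1), upper limit = Beta(0.975; x + 1, n − x). With x = 0 the lower limit is 0.

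**Step 1: reproduce the plan's own figures.**

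| Rate | x of 600 | Computed CI (%) | Table 4 |
|---|---|---|---|
| 1% | 6 | 0.37 to 2.16 | 0.4 to 2.2 |
| 2% | 12 | 1.04 to 3.47 | 1.0 to 3.5 |
| 3% | 18 | 1.79 to 4.70 | 1.8 to 4.7 |
| 4% | 24 | 2.58 to 5.89 | 2.6 to 5.9 |
| 5% | 30 | 3.40 to 7.06 | 3.4 to 7.1 |
| 10% | 60 | 7.72 to 12.68 | 7.7 to 12.7 |
| 15% | 90 | 12.24 to 18.11 | 12.2 to 18.1 |
| 20% | 120 | 16.87 to 23.43 | 16.9 to 23.4 |

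All eight rows agree, so the same method can be applied directly to subjects with a Grade 3 AE.

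**Step 2: same risk, different share of records (assumed counts).** Let 12 of 600 vaccinees have one Grade 3 AE each.

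- Subject level: 12/600 = 2.0%, exact 95% CI 1.04 to 3.47.
- Share of records if 100 AEs are recorded: 12/100 = 12%.
- Share of records if 300 AEs are recorded: 12/300 = 4%.

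The share differs threefold while the risk per vaccinee is identical.

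**Step 3: same share of records, different risk (assumed counts).** Let 5% of records be Grade 3.

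- 60 AEs, 3 Grade 3 records, all in one subject: 1/600 = 0.17%, CI 0.00 to 0.93.
- 240 AEs, 12 Grade 3 records in 12 subjects: 12/600 = 2.0%, CI 1.04 to 3.47.

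The share is the same but the risk differs 12-fold.

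**Step 4: what the event count still tells the reader.** Item 4 prints the number as well as the percentage, and SAP 6.1 reports the size of the safety set. Grade 3 events divided by N can only equal or exceed the proportion of subjects. In step 2 it is exact (12/600 = 2.0%). In the first case of step 3 it gives 3/600 = 0.5% against a true 0.17%. It is an upper bound on the observed proportion and carries no CI.

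**Step 5: what a subject-level table would give.**

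| Subjects with a Grade 3 AE (assumed) | n = 600: % (95% CI) | n = 576: 95% CI |
|---|---|---|
| 0 | 0 (0 to 0.61) | 0 to 0.64 |
| 3 | 0.5 (0.10 to 1.45) | 0.11 to 1.51 |
| 6 | 1.0 (0.37 to 2.16) | 0.38 to 2.25 |
| 12 | 2.0 (1.04 to 3.47) | 1.08 to 3.61 |
| 30 | 5.0 (3.40 to 7.06) | 3.54 to 7.35 |

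Even with no Grade 3 event, the table would bound the risk at about 0.6%. A share of records cannot do that.

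**The case against.** Several points on the other side are sound and limit the claim.

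- **The denominator is inferred.** SAP item 4 does not state one. Protocol 10.5.2.1 uses similar wording for a tabulation based on the number of vaccinated subjects. The record-based reading is still the more natural one, because item 1 of the same SAP section names subjects and events separately and items 4 and 5 name only AEs. It remains a reading.
- **The table shells are not shown.** The SAP appendix refers to mock-up TLFs, and a subject-level intensity table there cannot be excluded. A reader might infer that the risk of a Grade 3 AE will never be estimated. The documents do not support that: they show only that the written text plans no such estimate. Protocol 10.4.1 also provides for individual data listings, and intensity is rated for each event, so the figure could be derived later. But its form would then be chosen with the data in view.
- **The event count is printed beside the percentage.** The threefold swing in step 2 affects only one of the two reported figures, and the count over N gives the bound in step 4.
- **No comparison of intensity between age groups is planned.** A reader might object that record shares mislead across the two groups. But the study is non-comparative, SAP section 6 analyses the groups separately, and the exploratory tests concern AE incidence.
- **Intensity is not singled out.** Outcome, relationship and medically attended visits are handled in the same way, and intensity is not a named endpoint. It is, however, the only one of these four in the objective.
- **The grading scale is redacted** in Protocol 7.2.2.2, so the label and rank of Grade 3 cannot be checked.

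That the study is descriptive does not answer the point. In a descriptive study the estimate and its CI are the result.

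**Conclusion.** The point holds in a limited form. Intensity belongs to the sole objective, but the SAP and protocol text plan it only as a number and percentage of AEs, without subject-level incidence or a CI. As written, the plan does not deliver the proportion of vaccinees with a Grade 3 AE or its precision.

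The size depends on counts that the documents do not give. In the assumed examples, one risk of 2.0% (1.0 to 3.5) corresponds to record shares of 4% or 12%, and one share of 5% corresponds to risks from 0.17% to 2.0%. The conclusion rests on reading items 4 and 5 as shares of records and on the shells adding nothing beyond the text.

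It would go too far to say that the objective is left unaddressed, since intensity is described overall and by PT. This is a cheap improvement and does not undermine the study.

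**What to change.** In SAP 6.3.2, for each study group (3 years and above; 6 to 35 months), add:

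1. The number and percentage of subjects by worst intensity, each subject counted once at the highest grade, with the safety analysis set as denominator.
2. The number and percentage of subjects with at least one Grade 3 AE, and with at least one Grade 3 ADR, overall and by PT, with exact 95% CIs by the method of Table 4.
3. A sentence stating that items 4 and 5 use AE records as denominator and are supportive.

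If the mock-up TLFs already contain such tables, the SAP text need only be brought into line with them.

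The cost is a short addition to the SAP and a few extra tables per group. No new data are needed, because the physician already records the maximum intensity of each event in the CRF (Protocol 7.2.2.2).

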### 6.3.3 Other Analyses

- ① The distribution of the following will be tabulated with descriptive statistics. Also, 95% confidence interval for the percentage will be estimated using the exact method.
  - Subjects by concomitant medication and pre-existing medical conditions
  - Subjects with concomitant medication by treatment purpose and treatment start date
  - Concomitant medication by treatment purpose and treatment start date
- ② The number of subjects with AE/ADR and the number of AE/ADR by the following will be calculated. Also, the incidence proportion and its 95% confidence interval using the exact method will be estimated.

dreamcis A TIGERMED COMPANY	CONFIDENTIAL : THIS DOCUMENT AND INFORMATION CONTAINED HEREIN IS PROPRIETARY TO COMPANY AND IS NOT TO BE DISCLOSED WITHOUT THE WRITTEN PERMISSION OF COMPANY.	Last Update Date 10-SEP-2021
STATISTICAL ANALYSIS PLAN(V5.0)		

- Concomitant medication and pre-existing medical conditions
- Treatment purpose
- Treatment start date

Note: Pre-existing medical conditions (yes/no) is defined as any significant pre-existing conditions or signs and/or symptoms present prior to the start of the study recorded in the general medical history/physical examination section of the CRF. Treatment purpose of concomitant medication is recorded on the CRF 'Is drug used for treating AE?' of concomitant medication section. Concomitant medication by treatment start date will be classified into yes/no depending on whether concomitant medication started before vaccination.

dreamcis A TIGERMED COMPANY	CONFIDENTIAL : THIS DOCUMENT AND INFORMATION CONTAINED HEREIN IS PROPRIETARY TO COMPANY AND IS NOT TO BE DISCLOSED WITHOUT THE WRITTEN PERMISSION OF COMPANY.	Last Update Date 10-SEP-2021
STATISTICAL ANALYSIS PLAN(V5.0)		

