6.3.4. Concomitant medication/vaccination

All concomitant medications/vaccinations according to local practice are allowed during the drug use investigation and administration of these should be documented in the CRF.

At each drug use investigation visit/contact, the physician should question the subject/subject's parent(s)/LAR(s) about any medication taken and vaccination received by the subject.

All concomitant medications/vaccinations, with the exception of vitamins and/or dietary supplements, are to be recorded in the CRF. This also applies to concomitant medication administered prophylactically in anticipation of reaction to the vaccination and any medication intended to treat an AE.

A prophylactic medication is a medication administered in the absence of any symptom and in anticipation of a reaction to the vaccination (e.g. an anti-pyretic is considered to be prophylactic when it is given in the absence of fever and any other symptom, to prevent fever from occurring [fever is defined as temperature ≥ 37.5 °C (99.5 °F) on oral/axillary/tympanic setting].

Similarly, concomitant medication administered for the treatment of an SAE, at any time, must be recorded on the CRF concomitant medication section and in the SAE report form, as applicable. Refer to Section 7.1.3 for the definition of a SAE.

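### SAP 6.3.3 item 1 puts an exact binomial 95% CI on what reads as a count of medication records; the interval is too narrow to the extent that subjects contribute several correlated records

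*SAP*

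**What the plan says.** SAP 6.3.3 item 1 puts one interval instruction over three tabulations: the "95% confidence interval for the percentage will be estimated using the exact method".

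- First bullet: "Subjects by concomitant medication and pre-existing medical conditions".
- Second bullet: "Subjects with concomitant medication by treatment purpose and treatment start date".
- Third bullet: it repeats the wording "concomitant medication by treatment purpose and treatment start date" but drops the reference to subjects.

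The note to the same section defines the two classifying attributes. On purpose: "Treatment purpose of concomitant medication is recorded on the CRF 'Is drug used for treating AE?' of concomitant medication section". On timing, a medication is "classified into yes/no depending on whether concomitant medication started before vaccination". Both describe a drug, not a person.

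Protocol 6.3.4 sets what enters these tables: "All concomitant medications/vaccinations, with the exception of vitamins and/or dietary supplements, are to be recorded in the CRF". Neither document limits a subject to one record, states a denominator for the third bullet, or mentions an adjustment for repeated records.

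SAP section 6 reserves the 6.3.3 analyses for the final report and analyses the two age groups separately.

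**The concern.** An exact (Clopper-Pearson) interval is the binomial interval. It has at least its nominal coverage when each unit counted is an independent yes/no outcome. Subjects can reasonably be treated that way, but several drugs taken by one subject cannot. Drugs given for the same AE share both a purpose and a start period, and long-term drugs will usually all have started before vaccination. If such records are pooled and counted as independent, the effective sample size is overstated.

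What is at stake is small but concrete. The final report could carry an interval labelled 95%, for the share of medications used to treat an AE or started before vaccination, that covers the true share less often than stated. The dependence arises within one person, so it would remain in a single-centre study. It is a separate matter from subjects clustering within centres.

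**Working it through.** **1. What exact means here.** Protocol Table 4 gives exact two-sided 95% limits for 600 subjects, and the protocol's reference list cites the Clopper-Pearson paper. With x events in n units:

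- lower limit = 2.5% quantile of Beta(x, n − x + 1)
- upper limit = 97.5% quantile of Beta(x + 1, n − x)

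At n = 600 these give 0.37–2.16 for 1% (printed 0.4–2.2), 3.40–7.06 for 5% (3.4–7.1), 7.72–12.68 for 10% (7.7–12.7) and 16.87–23.43 for 20% (16.9–23.4). All eight rows agree to the printed decimal. The method is thus a binomial interval, and the protocol applies it to subjects.

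**2. Unit of the third bullet.** If it also counted subjects it would duplicate the second bullet. Its attributes are recorded per drug. The natural unit is the medication record.

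**3. Size of the effect.** Let m be records per subject and ρ the within-subject correlation. The variance of the pooled percentage is inflated by

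DEFF = 1 + (E[m²]/E[m] − 1)·ρ,

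and a valid interval must be wider by about √DEFF. The documents give neither m nor ρ, so both are assumed. With m = 1 + Poisson(λ), the bracket equals λ + λ/(1 + λ). For example, λ = 1 (mean 2) gives 1.5, so at ρ = 0.5 DEFF = 1.75 and √DEFF = 1.32.

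Coverage of the unadjusted exact 95% interval was simulated under further assumptions: 150 or 240 subjects with at least one medication, a true share of 20% or 50%, beta-binomial records, and 8,000 runs per cell. Ranges are over these four settings.

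| Mean drugs per subject | ρ = 0 | ρ = 0.1 | ρ = 0.3 | ρ = 0.5 | √DEFF at ρ = 0.5 |
|---|---|---|---|---|---|
| 1.2 | 96% | 95–96% | 94–95% | 93–94% | 1.09 |
| 1.5 | 96% | 95% | 93% | 91% | 1.19 |
| 2 | 95–96% | 94–95% | 90–91% | 87–88% | 1.32 |
| 3 | 95–96% | 92% | 86–87% | 81–82% | 1.53 |

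At ρ = 0.8 coverage is about 93%, 88–89%, 82–83% and 74–75% down the rows. A separate simulation (300 subjects, true share 30%, mean 3 drugs) gave 92.2%, 86.1%, 80.9% and 74.3% at ρ = 0.1, 0.3, 0.5 and 0.8.

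**4. Illustration.** Take 300 subjects with exactly 3 records each and 30% observed. The exact interval on 900 records is 27.0–33.1%, a width of 6.1 points. At ρ = 0.5, DEFF = 1 + (3 − 1) × 0.5 = 2, and the width needed is about 6.1 × 1.41 = 8.6 points.

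**The case against.** **The unit is inferred.** The SAP states no denominator for the third bullet, and the content of its appendix of mock-up tables is not available to check. This stands as a caveat. The record-level reading is still the natural one, and the text as written attaches the exact interval to it.

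**The shortfall is conditional.** A reader might infer that the interval is certainly too narrow. The documents do not support that. Protocol 6.3.4 shows that several records per subject are possible, not that they are common. A subject on long-term medication who also takes a drug for an AE supplies discordant records, which lowers the correlation. The exact method is itself slightly conservative and absorbs mild clustering: the table shows almost no loss at a mean of 1.2 drugs, or at ρ = 0.1 with up to 2 drugs. This objection stands in full and fixes how the point must be worded.

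**Apparent precision.** A reader might also infer that the record-level table would look more precise than the subject-level one. That depends on the denominator of the second bullet, which is unstated too. If it were 600 subjects, 120/600 gives 16.9–23.4%, while 45/225 records (150 subjects at a mean of 1.5) gives 15.0–25.8%, which is wider. The inference is not supported.

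**Consequence.** The table is descriptive, and no test, threshold or safety conclusion uses the interval. That is correct and limits the importance of the point. It does not make the method suitable for clustered records.

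**Conclusion.** The point holds in conditional form and is minor. On its natural reading, the third bullet of SAP 6.3.3 item 1 receives a binomial interval for records that are not independent. How far coverage falls below 95% rests on two quantities that the documents do not give. Under the assumptions above it runs from about 95%, with close to one drug per subject or correlation of 0.1 or less and few drugs, to about 80% with a mean of 3 drugs and correlation 0.5. It would be lower only under stronger correlation.

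The first two bullets count subjects, and the exact interval is suitable there. The AE and SAE endpoints are not affected, and neither is any point estimate.

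**What to change.** In SAP 6.3.3 item 1, restrict the exact 95% CI to the two bullets whose unit is the subject. For the third bullet, state that the unit is the medication record, define the denominator, and report number and percentage only. SAP 6.3.2 items 4 and 5 already do this for event-level counts.

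If an interval is wanted for the third bullet, use one clustered on subject: a cluster-robust (Taylor linearisation) interval, for example from SAS PROC SURVEYFREQ with subject as the cluster, or a bootstrap that resamples subjects.

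The cost is one sentence in the SAP and one column dropped, or one procedure changed, in the final-report table. No new data are needed. The downside is that the third tabulation has no CI, or a wider one.

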## Appendix

Mock up TLFs
